9.2.3 Medical History

Medical history will be coded by using the Medical Dictionary for Regulatory Activities (MedDRA). For the FAS, medical history will be summarized descriptively by System Organ Class (SOC) and Preferred Term (PT). The corresponding data listing will also be provided.

In addition, the number of subjects reported to have had positive cultures for respiratory pathogens within the 2 years prior to screening (i.e., answered yes on the respiratory microbiology form) will be summarized for the FAS. The corresponding data listing will be provided.

9.2.4 Prior and Concomitant Medications

Medications will be coded using the World Health Organization Drug Dictionary (WHO-DD) and categorized as follows:

Prior medication: any medication that was administered during the 56 days before the first dose of study drug in the Treatment Period but not in the Run-in Period. For subjects who discontinued during the Run-in Period and whose first dose of study drug in the Treatment Period is not available, prior medication will be any medication that was administered during the 56 days before the last dose of study drug in the Run-in Period but before the first dose in the Run-in Period.

Concomitant medication during the Run-in Period: medication continued or newly received during the TE period for the Run-in Period.

Concomitant medication during the Treatment Period: medication continued or newly received during the TE period for the Treatment Period.

Post-treatment medication: medication continued or newly received after:

- the TE period for the Run-in Period if the subject did not receive study drug in the Treatment Period.
- the TE period for the Treatment Period for subjects who received study drug in the Treatment Period.

A given medication may be classified as a prior medication, a concomitant medication, or a post treatment medication; both prior and concomitant; both concomitant and post treatment; or prior, concomitant, and post treatment.

If a medication has a missing or partially missing start/end date or time and if it cannot be determined whether it was taken before the first dose of study drug, concomitantly during the TE Period, or after the TE Period, it will be considered in all 3 categories of prior, concomitant, and

post treatment medication. Details for imputing missing or partial start and/or stop dates of medication are described in [Appendix B](#).

Prior medications and concomitant medications during the Treatment Period will be summarized descriptively for FAS using frequency tables by: 1) treatment group and overall, preferred name (PN); and 2) treatment group and overall, anatomic class (ATC) level 1, ATC level 2, and PN.

The number of subjects who used hormonal therapy concomitantly will be summarized by treatment group based on the Safety Set for the Treatment Period.

Prior and concomitant medication during the Run-in Period will be summarized together in one summary table. Post-treatment medications will be listed in the all medication listing.

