**Table 3-1 Study VX18-445-109: Screening**

Event/Assessment	Screening Visit Day -56 to Day -29	Comments
ICF and assent (when applicable)	X	
Inclusion and exclusion criteria review	X	
Demographics	X	
Medical history	X	
CFQ-R	X	Completed before the start of any other assessments (except signing ICF) scheduled for that visit.
CFTR genotype	X	If the screening CFTR genotype result is not received before enrollment, a previous CFTR genotype laboratory report may be used to establish eligibility. Subjects who have been enrolled and whose screening genotype does not confirm eligibility must be discontinued from the study.
FSH	X	Measured for any suspected postmenopausal female with at least 12 months of continuous spontaneous amenorrhea.
Serum pregnancy test (all female subjects)	X	
Hematology	X	
Coagulation	X	
Serum chemistry	X	
Urinalysis	X	
Weight and height	X	Measured with shoes off.
Ophthalmologic examination	X	Only conducted for subjects who are <18 years of age on the date of informed consent.
Complete physical examination	X	
Vital signs and pulse oximetry	X	Collected after the subject has been at rest for at least 5 minutes.
Standard 12-lead ECG	X	Performed after the subject has been at rest for at least 5 minutes.
Spirometry	X	Performed pre- or post-bronchodilator.
Medications review	X	
Sweat chloride	X	
AEs and SAEs	Continuous from signing of ICF through Safety Follow-up Visit	
AE: adverse event; CFQ-R: Cystic Fibrosis Questionnaire-Revised; FSH: follicle stimulating hormone; ICF: informed consent form; SAE: serious adverse event		

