##### **9.1.5.1 Discontinuation During the Run-in Period**

Subjects who prematurely discontinue study drug treatment during the TEZ/IVA Run-in Period will not be randomized or participate in the Treatment Period. These subjects will complete an ETT Visit and Safety Follow-up Visit (as applicable; see Section 9.1.5). The Safety Follow-up Visit will be their last visit in the study.

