## 9.5 Prior and Concomitant Medications

Information regarding prior and concomitant medications, including CF medications, other medications, and herbal and naturopathic remedies, will be collected from each subject's source documentation for medications taken within 56 days before the Screening Visit through completion of study participation, as defined in Section 9.1.7.

For subjects who are screened, but are not subsequently randomized into the Treatment Period, details of prior medication will be documented only in the subjects' source documents.

- Subjects should remain on a stable treatment regimen for their CF from 28 days before the TEZ/IVA Run-in Period/Day -28 through completion of study participation. Stable treatment regimen is defined as the current treatment regimen for CF that subjects have been following for at least 28 days before the TEZ/IVA Run-in Period/Day -28. Subjects may remain on Vertex CFTR modulators (investigational or approved) during the Screening Period and may transition directly to the TEZ/IVA Run-in/Day -28 without a washout (Table 9-2). Subjects

should not initiate long-term treatment with new medication from 28 days before the TEZ/IVA Run-in Period/Day -28 through completion of study participation. Guidelines for stable treatment regimens for CF are as follows:

- o Subjects who are taking inhaled tobramycin or other chronically inhaled antibiotics should remain on that regimen throughout the study.
  - o Subjects who cycle onto and off of an inhaled antibiotic should continue on their prior schedule. The timing of the first dose of study drug on the Day 1 Visit should be synchronized as closely as possible (e.g., not more than  $\pm 3$  days) to the first day in the cycle onto the inhaled antibiotic.
  - o Subjects who alternate between 2 different inhaled antibiotics should remain on the same cycling schedule during the study. The timing of the first dose of study drug on the Day 1 Visit should be synchronized as closely as possible (e.g., not more than  $\pm 3$  days) to the first day in the cycle onto 1 of the inhaled antibiotics.
- Subjects may receive doses of prednisone or prednisolone of up to 10 mg/day chronically, or up to 60 mg daily for up to 5 days.
  - VX-445 may inhibit OATP1B1 and OATP1B3, which may increase the exposure of medicinal products that are substrates for these transporters. Substrates such as statins, glyburide, nateglinide, and repaglinide should be used with caution.

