#### **12.3.2.3 Prior and Concomitant Medications**

Medications will be coded using the World Health Organization Drug-Dictionary and categorized as follows:

- **Prior medication:** any medication that was administered during the 56 days before the first dose of study drug in the Treatment Period but not in the Run-in Period. For subjects who discontinue during the Run-in Period and whose first dose of study drug in the Treatment Period is not available, prior medication will be any medication that was administered during the 56 days before the last dose of study drug in the Run-in Period but before the first dose in the Run-in Period
- **Concomitant medication during the Run-in Period:** medication continued or newly received during the TE Period for the Run-in Period
- **Concomitant medication during the Treatment Period:** medication continued or newly received during the TE Period for the Treatment Period
- **Post-treatment medication:** medication continued or newly received after:

- the TE Period for the Run-in Period if the subject did not receive study drug in the Treatment Period
- the TE Period for the Treatment Period for subjects who received study drug in the Treatment Period

A given medication may be classified as a prior medication, a concomitant medication, or a post-treatment medication; both prior and concomitant; both concomitant and post-treatment; or prior, concomitant, and post-treatment. If a medication has a missing or partially missing start/end date or time and if it cannot be determined whether it was taken before the first dose of study drug, concomitantly during the TE Period, or after the TE Period, it will be considered in all 3 categories of prior, concomitant, and post-treatment medication.

Prior medications and concomitant medications will be summarized descriptively by Preferred Name based on the FAS. Post-treatment medications will be provided separately in an individual subject data listing.

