Appendix B: Imputation Rules for Missing Prior/Concomitant Medication Dates

Imputation rules for missing or partial medication start/stop dates are defined below:

1. Missing or partial medication start date:
 - a. If only DAY is missing, use the first day of the month.
 - b. If DAY and Month are both missing, use the first day of the year.
 - c. If DAY, Month and Year are all missing, use a date before the first dose date (in practical, use the informed consent date).
2. Missing or partial medication stop date:
 - a. If only DAY is missing, use the last day of the month.
 - b. If DAY and Month are both missing, use the last day of the year.
 - c. If DAY, Month and year are all missing, assign ‘continuing’ status to stop date (in practical, use the End of Study Date to impute).

In summary, the prior, concomitant, or post categorization of a medication is described below.

Table 12-2 Prior, Concomitant, and Post Categorization of a Medication

Medication Start Date	Medication Stop Date			
	< First Dose Date of Run-in TE Period	≥ First Dose Date and < End Date of Run-in TE Period	≥ First Dose Date and ≤ End Date of Treatment TE Period	> End Date of Treatment TE Period
< First dose date of Run-in TE period	P	PC1	PC1C2	PC1C2A
≥ First dose date and < End date of Run-in TE Period	-	C1	C1C2	C1C2A
≥ First dose date and ≤ End date of Treatment TE Period	-	-	C2	C2A
> End date of Treatment TE Period	-	-	-	A

P: Prior; C1: Concomitant during the Run-in Period; C2: Concomitant during the Treatment Period; A: Post

Imputation rules for missing and/or partial dates of non-pharmacological treatment/procedure will follow the same imputation rule.

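### Does the missing 56-day limit in SAP Table 12-2 make the prior-medication summaries unreliable?

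*SAP*

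**What the plan says.** Two places in the SAP classify medication.

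- **SAP 9.2.4** defines prior medication as any medication "administered during the 56 days before the first dose of study drug in the Treatment Period but not in the Run-in Period". Protocol 12.3.2.3 has the same rule: "any medication that was administered during the 56 days before the first dose of study drug in the Treatment Period", again leaving out the run-in.
- **SAP Appendix B, Table 12-2**, is introduced with "In summary, the prior, concomitant, or post categorization of a medication is described below". It gives the code P to a medication whose start and stop dates both precede the first run-in dose. It shows no lower date limit.

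A third place governs what is recorded. Protocol 9.5 collects "medications taken within 56 days before the Screening Visit through completion of study participation", and Table 3-1 sets "Screening Visit Day -56 to Day -29".

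Run-in discontinuers have their own definition. SAP 9.2.4 begins it "For subjects who discontinued during the Run-in Period and whose first dose of study drug in the Treatment Period is not available" and counts 56 days back from the last run-in dose. Protocol 9.1.5.1 says these subjects "will not be randomized or participate in the Treatment Period". Protocol 9.5 says that, for subjects screened but "not subsequently randomized into the Treatment Period, details of prior medication will be documented only in the" source documents.

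**The concern.** The collection window is anchored to Screening and the 9.2.4 definition to Day 1, so more is recorded than the definition covers. For a drug that ended early in the collection window, the text and the table disagree. The fallback in 9.2.4 that puts a medication into all three categories does not help, because it applies only when missing or partial dates leave the timing undetermined.

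Two programmers could therefore produce different prior-medication counts by arm. Vertex CFTR modulators are restricted only from Day -28 (protocol Table 9-2), so a modulator stopped early could appear in the prior-medication tables or drop out of them depending on the rule. The stratification factor, the model covariate and the subgroup hold only yes or no for modulator use at Screening, so they do not show which modulator it was.

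For run-in discontinuers, the SAP appears to define a variable from data that the protocol keeps at the site.

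**Working it through.** The plan states no figure on this point, so there is none to reproduce. The check is study-day arithmetic followed by tracing where the category is used.

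**Inputs.** There is no Day 0: Day -1 is the day before Day 1 (protocol 9.1.2). Screening falls on Day -56 to Day -29 (Table 3-1) and the window can be extended by two weeks (9.1.1.3), so at the earliest on Day -70. The run-in starts on Day -28 ± 1 day (Table 3-2).

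**Step 1: the window in the text.** Fifty-six days before Day 1 is Day -56. Up to Day -29 that is 56 − 29 + 1 = 28 days, or 27 to 29 days with the ± 1 day on the run-in start. I read the exclusion of the run-in as a limit on the days counted, since 9.2.4 allows a medication to be both prior and concomitant.

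**Step 2: the window recorded.** Collection starts at the Screening day minus 56.

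| Screening | Collection starts | Days recorded to Day -29 | Of these, before Day -56 |
|---|---|---|---|
| Day -29 | Day -85 | 85 − 29 + 1 = 57 | 85 − 57 + 1 = 29 |
| Day -56 | Day -112 | 112 − 29 + 1 = 84 | 112 − 57 + 1 = 56 |
| Day -70 | Day -126 | 126 − 29 + 1 = 98 | 126 − 57 + 1 = 70 |

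These are calendar days. They say nothing about how many records or subjects fall in the gap.

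**Step 3: test records with known dates, all started before the run-in.**

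| Last day of use | SAP 9.2.4 | Table 12-2 |
|---|---|---|
| Day -60 | no category | P |
| Day -57 | no category | P |
| Day -56 | prior | P |
| Day -30 | prior | P |

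The rules part only for a medication whose entire recorded use ended by Day -57. A medication continuing into the run-in is prior and concomitant under both. The difference goes one way: the table can add prior records but never remove any.

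**Step 4: what can lie in the gap.** Protocol 9.5 asks for a stable CF regimen from 28 days before Day -28, that is, from Day -56. The regular CF treatment in that regimen is taken on or after Day -56 and is prior under both rules. So is a Vertex modulator used during the four weeks before the run-in. The gap holds short courses and treatments already given up.

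**Step 5: where the category is used.**

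- The preferred-name table and the table by ATC level and preferred name, both on the FAS (SAP 9.2.4): counts could differ.
- The combined table of prior and run-in concomitant medication: counts could differ.
- The listing of all medications: the record is there either way, and only its label could differ.
- The seven prior-use rows in SAP 9.2.2: these carry their own anchor, the first Treatment Period dose, and do not refer to Table 12-2.
- The primary and key secondary models (SAP 9.3.1.2, 9.3.2.2): the covariates are baseline ppFEV₁, age group and modulator use at Screening. Prior-medication status is not among them.
- The rash subgroup by hormonal therapy (SAP 9.4.1.1): this uses concomitant medication only.

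**Step 6: run-in discontinuers.** Their window runs from the last dose minus 56 to Day -29. A last dose on Day -28 gives Day -84 to Day -29, or 56 days; a last dose on Day -1 gives Day -57 to Day -29, or 29 days. They cannot be in the FAS, which requires randomization and a Treatment Period dose. Protocol 12.3.2.3 bases the medication summaries on the FAS. The one table their definition could reach is the run-in table, for which SAP 9.2.4 names no analysis set.

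**The case for a change.** The best case for a change is that Table 12-2 is what a programmer will code from, it omits a limit that the text imposes, and no sentence says which prevails. SAP 3.1 declares no departure from the protocol, so the table cannot be read as a deliberate change. A footnote would cost almost nothing.

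The mismatch stands: the step 3 results follow directly from the two rules. The ambiguity is narrower than it looks, however. The definition appears in the same terms in the protocol and the SAP. SAP 9.2.4 refers to Appendix B for imputing missing dates, and the table there presents itself as a summary. An analyst who finds the two at odds would apply the definition. Collecting more than is tabulated is no conflict either, because protocol 9.5 sets what is recorded and does not classify it.

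The modulator argument carries little weight. It concerns only a modulator stopped by Day -57 yet inside the look-back, nothing in the documents shows that such a subject enrolled, and the listing would still show the drug.

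For run-in discontinuers, the definition is in protocol 12.3.2.3 as well as in the SAP. The tension with protocol 9.5 is therefore internal to the protocol, and it reaches no FAS table. Deleting the definition from the SAP would itself create a departure from the protocol.

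**Conclusion.** No change to the plan follows. Table 12-2 has lost the 56-day limit of the definition it summarises. The consequence is confined to medications with known dates that ended on or before Day -57: some descriptive counts of prior medication could be higher under the table than under the text, and a listing label could differ. How many records this touches cannot be worked out from the documents.

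Whichever rule is followed, the estimates, tests and safety summaries are the same, because none of them uses prior-medication status. A harmonising footnote would tidy the SAP without improving power, bias, safety or the trial's ability to answer its question. The point can be settled in the programming specifications by following the definition that both documents share.

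This rests on two assumptions: that the modulator covariate comes from the Screening status used for stratification, as SAP 9.3.1.2 describes it, and that early-ending records stay in the listing of all medications.

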9.2.5 Study Drug Exposure

Study drug exposure will be summarized for the Treatment Period based on the Safety Set for the Treatment Period, and will be presented by treatment group.

Duration of study drug exposure (in weeks) will be calculated as: (last dose date of study drug in the Treatment Period – first dose date of study drug in the Treatment Period + 1)/7, regardless of study drug interruption, and will be summarized descriptively.

Study drug exposure (in weeks) will be summarized descriptively by the number of subjects (n), mean, SD, median, min, and max. It will also be summarized by interval, using counts and percentages.

9.2.6 Study Drug Compliance

Study drug compliance will be summarized for the Treatment Period based on the FAS, and will be presented by treatment group and overall.

Study drug compliance will be calculated as: $100 \times [1 - (\text{total number of days of study drug interruption during the Treatment Period}) / (\text{duration of study drug exposure in days during the Treatment Period})]$. A study drug interruption on a given day is defined as an interruption of any study drugs on that day. A study drug interruption that continues through the end of the study participation (i.e., subject does not resume study drug before the end of the study participation) will not be included in the compliance calculation.

Study drug compliance will be summarized descriptively by the number of subjects (n), mean, SD, median, min, and max. It will also be summarized in categories: <80% and ≥80% using frequency tables.

9.2.7 Important Protocol Deviations

An important protocol deviation (IPD) is a deviation that may significantly affect the completeness, accuracy, or reliability of the study data or that may significantly affect a subject's rights, safety, or well-being. IPD rules will be developed and finalized before database lock.

The protocol deviations that should be considered as potential IPDs include, but are not limited to:

- Subject was enrolled in the study despite the violation of inclusion/exclusion criteria
- Subject was less than 80% compliant with study drug for non-safety reasons
- Subject received prohibited concomitant medications

- Subject received the wrong treatment or incorrect doses

Occurrence of any of these events should be considered as potential IPDs, but a blinded team should categorize them as IPDs only if they have the potential to significantly affect the completeness, accuracy, or reliability of the study data or that may significantly affect a subject's rights, safety, or well-being.

IPDs (from the clinical database or from the site deviation log) will be summarized descriptively based on the FAS and presented by treatment group and overall. Additionally, IPDs will be provided in an individual subject data listing.

9.3 Efficacy Analysis

Unless otherwise defined, all efficacy analyses described in this section will be based on the FAS.

9.3.1 Analysis of Primary Efficacy Variable

9.3.1.1 Definition of Variable

The primary efficacy variable is the absolute change in CFQ-R respiratory domain (RD) score from baseline through Week 24.

Cystic Fibrosis Questionnaire-Revised (CFQ-R): The CFQ-R^{3,4,5} is a validated CF-specific instrument that measures quality-of-life domains. This study utilizes three different versions of CFQ-R:

- CFQ-R for Children ages 12 and 13
- CFQ-R for Adolescents and Adults (subjects 14 years and older)
- CFQ-R for Parents/Caregivers (subjects 13 years and younger)

In all three versions, specific question belonging to a domain is scored 1, 2, 3, or 4. The CFQ-R domain score, e.g., physical domain score or respiratory domain score, is defined as a scaled score as follows:

Scaled score for a domain = $100 \times (\text{mean}(\text{scores of all questions in the domain}) - 1)/3$, where the score from a negatively phrased question is first reversed, i.e., reversed score = $5 - \text{actual score}$, so that 1 always represents the worst condition and 4 the best condition. The (scaled) domain score ranges from 0 (worst condition) to 100 (best condition). The scaled score for a specific domain will not be calculated if more than half of the questions in the domain have missing scores.

The (scaled) domain score from the CFQ-R for Children ages 12 and 13 and for Adolescent and Adults will be pooled for the analysis purpose.

9.3.1.2 Primary Analysis

The primary analysis will be performed using a mixed-effects model for repeated measures (MMRM) with the absolute change from baseline at each post-baseline visit as the dependent variable. The model will include treatment group, visit, and treatment-by-visit interaction as fixed effects, with continuous baseline ppFEV₁, age at Screening (<18 versus ≥18 years of age), and CFTR modulator use at Screening (yes versus no) as covariates. The model will be estimated using restricted maximum likelihood. Denominator degrees of freedom for the *F*-test for fixed

effects will be estimated using the Kenward-Roger approximation². An unstructured covariance structure will be used to model the within-subject errors. If the model estimation does not converge, a compound symmetry covariance structure will be used instead. Conditional on the observed data and covariates, missing data will be assumed to be missing at random; no additional imputation of missing data will be performed.

The primary result obtained from the model will be the estimated treatment difference through Week 24 (defined as the average of Weeks 4, 8, 16, 24). The least squares (LS) mean estimate with a 2-sided 95% CI and a 2-sided P value will be provided. The treatment difference at each post-baseline visit, obtained from the model, will also be provided.

The LS mean (with SE) obtained from the MMRM analysis at each post-baseline visit up to Week 24 will be plotted by treatment group. In addition, the post-baseline raw values and the absolute change from baseline at each post-baseline visit up to Week 24 will be summarized descriptively (n, mean, SD, median, minimum, and maximum).

The primary analysis will include all available CFQ-R RD data obtained at clinic and at home. An additional analysis using data before the outbreak of COVID-19 (defined as March 2, 2020) may be performed, if the CFQ-R RD data before COVID-19 are inconsistent with CFQ-R data during COVID-19. In addition, similar additional analysis using the CFQ-R RD data obtained at clinic only may be performed, if the CFQ-R RD data obtained at home due to COVID-19 are inconsistent with the CFQ-R RD data obtained at clinic. Such additional analysis results should be interpreted with caution due to reduced sample size.

